7.4. Secondary Mechanistic Endpoints

The following mechanistic endpoints will be assessed using the ITT sample:

- Incidence and kinetics of DSA and autoantibodies, specifically Collagen V (CoIV) and κ 1T
- Frequency, kinetics, phenotype and function of peripheral B cells
- Frequency, kinetics and cytokine profiles of allo and auto-reactive T cells
- Incidence and quantity of B cells and B cell proximity to other cells in the graft tissue

We will correlate pre and/or post-transplant serum reactivity to each autoantigen and to donor HLA with our primary endpoint to prospectively and independently test the hypothesis that autoantibodies can be used as predictors of incipient injury. We will also correlate the presence of serum antibodies with positive C4d staining of the graft tissue (to be collected as part of the clinical component of the study).

To test the hypothesis that rituximab prevents induction of de novo autoantibodies and or DSA, we will compare titers of autoantibodies (or DSA) between the rituximab and control groups. Development of antibodies to either DSA or self-antigens or both and the kinetics of antibody development (time course following transplantation) will be correlated with clinical evidence of AMR and BOS as determined in the clinical part of study described above and the ISHLT criterion. While the absolute numbers of patients in each group with preexisting autoantibodies or DSA is anticipated to be small (thus limiting power) we will compare and report pre vs post-transplant titers in each case to determine if rituximab impacts preexisting antibody.

The results will be analyzed for development of PGD, development of DSA, diagnosis of AMR and BOS. In addition we will also determine any correlation which may exist between the strength of antibodies detected for DSA, HLA and each antibody to self-antigens either alone or cumulatively and clinical outcomes such as PGD, AMR and BOS.

We will analyze DSA and each type of antibody separately. The DSA and autoantibody data will consist of binary (positive/negative) or ordinal (negative/weak positive/strong positive) responses measured repeatedly at scheduled and unequally spaced intervals. With these features of the data and at this sample size, it may not be feasible to obtain estimates of treatment effect at each time-point using a single statistical model with rituximab and time main effects and their interaction as covariates. Therefore, we will describe the treatment effect over the course of the follow-up period.

The hazard ratio for the association between development of antibodies and clinical outcomes (the endpoint and its components, and the secondary incidence endpoints) will be estimated with its 90% confidence interval using a Cox proportional hazard model with presence or absence of antibodies as time-dependent repeated measures covariates, stratified by treatment group. We will model the association of each antibody on each outcome separately and in combination.

As permitted by the data, we will estimate odds ratios with 90% confidence intervals for the associations between each of the various serum antibodies and C4d staining of the graft tissue. We will estimate these odds ratios at each time point between each pair of antibodies and each antibody and C4d result, both cross-sectional, and cumulative, in which case we would treat any subject with a current or prior positive result as positive for that particular antibody.

Immunophenotyping of B cell and T cell subsets from flow cytometry will be examined. B cell and T cell fractions will be compared between treatment groups within a repeated measures mixed model framework while utilizing samples from the pre-transplant, weeks 4-6, and months

3, 6, 12 and 18 time points. P-values from Tukey's HSD test will be reported to account for multiple comparisons of the mean cell fractions between groups at the various time points.

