Rituximab is a chimeric mouse/human monoclonal antibody approved as early as 1997 for use in Non-Hodgkin's Lymphoma, Chronic Lymphocytic Leukemia, Rheumatoid Arthritis (RA) in combination with methotrexate in adult patients with moderately-to severely-active RA who have inadequate response to one or more TNF antagonist therapies, Wegener's Granulomatosis and Microscopic Polyangiitis in combination with glucocorticoids. Rituximab targets CD20, a cell surface expressed protein found immature, transitional, mature and memory B cells but is absent on antibody producing plasma cells. While its exact mechanism of action is not fully understood, multiple studies in adults with autoimmune diseases such as Systemic Lupus Erythematosus (SLE) or RA showed that rituximab markedly depletes CD19+HLA-DR+⁵⁷ and memory CD19+CD27+ B cells.⁵⁸ Switched memory B cells (CD27+IgD-) are relatively spared compared to CD27-IgD+ naïve B cells and CD27+IgD+ unswitched B cells.⁵⁸ Further in RA patients, responders to rituximab therapy showed a significant decrease in CD19+CD27+ memory B cells compared to non-responders indicating that response may be impacted by the subset of B cells affected.⁵⁷ One important consequence of rituximab-induced B cell depletion is that the host B cell repertoire repopulates over the ensuing 3-6 months. This reconstitution process appears to recapitulate B cell ontogeny, where immature B cells undergo negative selection on stromal cells in the bone marrow and emerge with a transitional phenotype into the periphery.⁵⁹ Transitional B cells, characterized by expression of CD38hiCD24hiIgD+CD27-CD10+/-,⁶⁰ require survival signals provided by the cytokines BAFF and APRIL and are key intermediaries in the development of the mature B cell repertoire. Evidence suggests that the transitional B cell population contains Breg and that transitional B cells are subject to mechanisms of self-tolerance in the periphery.

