2.4. Clinical Studies

The funded and ongoing CTOTC-03 trial is a prospective, observational study to evaluate the impact of respiratory viral infections on the development of allo- and autoreactivity in pediatric lung transplant recipients. The team has laboratory results on 36 patients thus far.

While positive class I (3%) or class II (0%) DSA pre-transplant were rare, significant numbers developed class I and class II DSA within 3 months post-transplant (**Figure 2**).

[figure not shown]

Autoantibodies to ColV and α 1T were detectable prior to transplant in 33% and 44% of subjects, respectively. Post-transplant, de novo DSA and autoantibodies to both self-antigens occurred frequently, with α 1T most common. Correlations between antibodies and outcomes have not been assessed to date.

These results indicate both allo- and autoantibodies develop frequently and early following pediatric lung transplantation supporting our contention that induction therapy targeting B cells will be required to prevent and/or eliminate these antibodies.

We analyzed recipient T cells for reactivity to donor antigens (when donor tissue was available) and to ColV and α 1T as putative autoantigens. We observed 9/26 (35%), 2/36 (6%) and 21/36 (58%) of the recipients exhibited significant frequencies of IFN γ producing cells to donor and/or autoantigens (ColV and α 1T) posttransplant, respectively.

To expand upon these techniques to test for IL-17 production (IL-17 has been associated with BOS in recent adult transplant recipients²⁵) with limited available cells from pediatric patients we developed a 2 color IFN γ /IL-17 ELISPOT assay (**Figure 3**).

CTOTC-03 tested for respiratory viral infections as a potential trigger for immune activation. We evaluated prospective serial nasopharyngeal (NP) and bronchoalveolar lavage (BAL) specimens and interrogated by respiratory multiplex PCR (Luminex xTAG) that identifies 17 viruses.

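### The test of whether rituximab prevents new autoantibody includes children who are already positive before transplant, so it does not isolate de novo induction

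*SAP*

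**What the plan says.** SAP 7.4 assigns the mechanistic endpoints to the ITT sample and gives one method for this hypothesis: "To test the hypothesis that rituximab prevents induction of de novo autoantibodies and or DSA, we will compare titers of autoantibodies (or DSA", with the comparison made between the two arms. Protocol 13.4.5 has the same text and names no narrower set of children. Neither section limits the comparison to children negative before transplant, adjusts for the pre-transplant titre, or says whether a child positive at baseline can count as developing an antibody. The only mention of pre-transplant immunity as a covariate is in SAP 7.2.3. There it is optional and concerns sensitivity analyses of the primary endpoint.

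The next step in SAP 7.4 is a separate before-and-after comparison, meant to show whether rituximab changes antibody that already exists. It carries the caveat that "the absolute numbers of patients in each group with preexisting autoantibodies or DSA is anticipated to be small (thus limiting power".

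Protocol 2.4 summarises the earlier observational study in children: "The team has laboratory results on 36 patients thus far". Autoantibodies to ColV and k-alpha-1 tubulin "were detectable prior to transplant in 33% and 44% of subjects, respectively". For DSA the picture differs: "While positive class I (3%) or class II (0%) DSA pre-transplant were rare".

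Protocol 9.1.2 uses pre-transplant serum to set baseline autoantibody titres, and Appendix 1 schedules that serum at visit 00.

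**The concern.** A child who already has an antibody before transplant cannot develop it de novo. If a third or more of the children are in that position, a between-arm comparison of all titres mixes two questions: does rituximab prevent new autoantibody, and does it change existing autoantibody? The result cannot be assigned to either.

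Reduced antibody development is the mechanism stated in protocol 1.1, and the effect on post-transplant immunity is the first secondary objective. A muddied answer here would weaken the mechanistic reading of the trial, whichever way the clinical result falls.

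Chance adds to the problem. Protocol 3.5 and 8.7.1 name no stratification by antibody status, so the arms may differ in baseline positivity.

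**Working it through.** **Inputs from the documents.** Pre-transplant positivity q is 0.33 (ColV) and 0.44 (tubulin), and 0.03 / 0 for class I / II DSA (protocol 2.4). There are 50 children randomised 1:1, so 25 per arm. The interval level is two-sided 90% (protocol 13.4), taken here as two-sided alpha 0.10.

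**Input not in the documents.** No de novo rate can be read. Protocol 2.4 says only that "de novo DSA and autoantibodies to both self-antigens occurred frequently", and its figure is not shown. I assume a control rate c of 30% to 60% among baseline-negative children, with 50% as the worked example, and a reduction by rituximab of 50% to 75%.

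**Step 1. The stated percentages.** The protocol gives no numerators. Out of 36, 12 is 33.3%, 16 is 44.4% and 1 is 2.8%, so the figures are consistent with that denominator. On those counts the exact 95% intervals are about 19% to 51% (ColV) and 28% to 62% (tubulin).

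**Step 2. Baseline positives per arm.** 25 × 0.33 = 8.25 and 25 × 0.44 = 11. For class I DSA, 25 × 0.03 = 0.75.

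**Step 3. Existing antibody persists in both arms.** All-child proportion positive = q + (1 − q) × de novo rate. With 50% against 25%:
- ColV: control 0.33 + 0.67 × 0.50 = 0.665; rituximab 0.33 + 0.67 × 0.25 = 0.4975. Risk ratio 0.75, risk difference 16.75 points.
- Tubulin: control 0.44 + 0.56 × 0.50 = 0.72; rituximab 0.44 + 0.56 × 0.25 = 0.58. Risk ratio 0.81, risk difference 14 points.
- Among baseline-negative children: risk ratio 0.50, risk difference 25 points.

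With the rate still halved but c varied from 30% to 60%, the all-child risk ratio runs from 0.81 to 0.73 (ColV) and from 0.86 to 0.78 (tubulin).

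**Step 4. Rituximab clears existing antibody and has no de novo effect.** Protocol 2.4 reports that 46.7% of tubulin-positive and 48.4% of ColV-positive adults became negative after rituximab plus IVIG. If that happens in the rituximab arm only, the all-child difference is q × clearance:
- ColV: 0.33 × 0.484 = 0.160.
- Tubulin: 0.44 × 0.467 = 0.205.

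**Step 5. Power, with existing antibody persisting.** Two-proportion test over the assumed range of control rates and reductions:

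| Antibody | All children, 25 per arm | Baseline-negative only |
|---|---|---|
| ColV | 0.17 to 0.71 | 0.27 to 0.88 (16.75 per arm) |
| Tubulin | 0.15 to 0.59 | 0.24 to 0.82 (14 per arm) |

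For DSA at 3%, with 45% against 22.5%, power is 0.49 in all children and 0.50 in negatives.

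**Step 6. Continuous titres.** The plan speaks of titres, so the check is repeated with a 1 SD effect in negatives only and positives lying 0 to 2 SD above untreated negatives. Unadjusted all-child power is 0.45 to 0.73 (ColV) and 0.34 to 0.59 (tubulin). Stratifying by baseline status gives 0.77 and 0.63. Restricting to negatives gives 0.89 and 0.84.

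**Step 7. Chance imbalance.** The SD of the between-arm difference in baseline positivity is √(2q(1 − q)/25): √(2 × 0.33 × 0.67/25) = 0.133 and √(2 × 0.44 × 0.56/25) = 0.140. These are about the size of the diluted differences in step 3.

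**The case against.** The strongest reply is that the section is loosely specified rather than wrong. Comparing titres fixes no model. Pre-transplant titres will be available, a before-and-after report is already planned, and SAP 7.4 admits that a full model over time may not be feasible. The endpoint is mechanistic, and protocol 13.4.5 files it under exploratory analyses. That lowers the stakes but does not close the gap: the one stated method for the de novo hypothesis has no baseline rule.

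A reader might also infer that the SAP pools all children because it expects pre-existing antibody to be rare, and that 33% and 44% contradict this. The documents do not support either inference. The caveat concerns absolute numbers per group and belongs to the before-and-after analysis. With 8.25 or 11 children per arm, 80% power at two-sided alpha 0.10 needs a difference of about 1.22 or 1.06 SD, from (1.645 + 0.842) × √(2/m). Calling that small and power-limiting is correct.

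A reader might further infer that pooling must bias towards no effect, since CD20 "is absent on antibody producing plasma cells". That is a reason to expect persistence, not proof of it. The adult clearance figures point the other way. They are uncontrolled and confounded by IVIG, and come from adults who had developed DSA, but they are the protocol's only figures on the question. Put into the 50% to 25% example, they raise the all-child difference to 0.1675 + 0.160 = 0.33 (ColV) and 0.14 + 0.205 = 0.35 (tubulin), above the 0.25 among negatives. The direction of error is therefore open.

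**Conclusion.** The point holds for the two autoantibodies. As written, the comparison does not isolate de novo induction, because about a third (ColV) and over two fifths (tubulin) of the children can be expected to be positive at the start.

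The size depends on what happens to existing antibody. If it persists in both arms, an assumed halving appears as a risk ratio of 0.75 or 0.81. If it is cleared in the rituximab arm only, at the adult rates, a difference of 16 or 20.5 points appears with no prevention at all. The de novo rates are assumptions, and the two prevalences rest on about 36 children.

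The point does not extend to DSA, where baseline positivity of 3% and 0% leaves the comparison almost unchanged. It does not affect the primary endpoint, the clinical secondary endpoints or the safety analyses. It should be corrected as a matter of clear specification of a secondary mechanistic analysis.

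**What to change.** In SAP 7.4 and protocol 13.4.5:

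1. For each autoantibody separately, define de novo as conversion from negative on the visit 00 serum. State whether a weak positive (protocol 9.1.2) counts as positive, and use the last serum before transplant where collection was repeated.
2. Compare arms among children negative for that antibody at visit 00, by time to first positive or proportion positive, with the 90% interval.
3. Adjust any titre comparison in all children for the visit 00 titre.
4. Report children positive at visit 00 by arm, as a separate analysis of the effect on existing antibody.
5. Keep the small-numbers caveat, which is right for that subset, and put the 33% and 44% figures beside it.

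The cost is wording only, since visit 00 serum is already scheduled and assayed. Each de novo analysis would use about 28 (50 × 0.56) to 33 (50 × 0.67 = 33.5) children instead of 50. Those left out carry no information on de novo antibody of that specificity. Under the persistence assumption the smaller set has more power, as steps 5 and 6 of the working show.

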Preliminary epidemiologic data revealed 23 of 31 (74%) of subjects had at least one positive viral specimen. The median time to virus-positive specimens was 65 days post-transplant (range 1-599). Rhino/enterovirus was recovered most frequently (40 episodes) compared to coronavirus (3), hMPV (1), influenza (2), RSV (2), adenovirus (1), parainfluenza (1). Rhino/enterovirus occurred throughout the year but the other viruses were detected in the winter/spring months. Along with previous infectious diseases epidemiology, we have the capacity to monitor for and respond to changes in the rates of infectious episodes in our patient population.

Development of Abs to HLA following Lung Transplant and its impact on the development of BOS:

Since 2006, the Washington University adult lung program and the [name] lab instituted serial analysis for development of Abs to donor mismatched HLA during the post-transplant period. All adult LTxR had negative donor cross-matches. Of 116 patients serially analyzed, 65 developed DSA (56%), with 52 in the first 90 days, again supporting our contention that early intervention will be required to prevent induction. To test the hypothesis that antibodies contribute to late graft injury, the [name] group used IVIG (500 mg/kg x 6 monthly doses) and rituximab (375 mg/m² x 1 dose) for desensitization. Of the 44 patients treated, 27 (61%) cleared the DSA, and 17 (39%) had persistent DSA. An additional 17 patients were treated with IVIG alone and 11 (65%) cleared the DSA. More importantly, patient and graft survival was significantly better in successfully desensitized patients (Figure 4) providing strong correlative evidence that DSA participate in the development of allograft injury.⁷⁸

[figure not shown]

Figure 4: Improved survival following clearance of DSA.

A critical role for Abs to self-Ags in the pathogenesis of BOS:

Among adult LTxR who developed DSA (n=57) and subsequently cleared DSA following Ab directed therapy (n=34), 9 patients nonetheless developed BOS. We detected persistence of Abs to self-Ags, CoIV and κ 1T in most of these individuals, strongly implicating pathogenic roles for Abs to self-Ags. As shown in **Figure 5**, the LTxR who cleared both Abs to HLA and self-Ags demonstrated improved freedom from BOS in comparison to patients that cleared only DSA but not Abs to self-Ags.

[figure not shown]

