3.1. Description of Study Design

This is a phase 2, prospective, multi-center, double-blind, randomized, placebo-controlled clinical trial in which 50 primary pediatric lung transplant recipients will be randomized (1:1) to receive either induction therapy with anti-CD20 mAb (375 mg/m²) IV or placebo (IV day 0 and day 12 post-transplant) plus standard of care immunosuppression (thymoglobulin induction, tacrolimus or equivalent, MMF or equivalent, and steroids). The study will randomize 50 primary pediatric lung transplant recipients from seven participating centers. Subjects will be screened, consented, and enrolled while on the UNOS waitlist. When the recipient has received the transplant and is deemed hemodynamically stable, randomization will occur.

[figure not shown]

Figure 9: Study Design

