7.1. Immunosuppression Medications

7.1.1. Protocol-mandated

7.1.1.1 Thymoglobulin® [Anti-thymocyte Globulin (Rabbit)]

All subjects will receive Thymoglobulin® induction therapy. Thymoglobulin® will be administered for 5 days as an intravenous infusion at a dose of 1.5 mg/kg/day beginning on the day of transplant.

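### Whether rituximab affects pre-existing antibody is to be judged from pre- versus post-transplant titres, with no between-arm contrast stated for children who are antibody-positive before transplant

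*SAP*

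**What the plan says.** SAP 7.4 and protocol 13.4.5 put two antibody questions in one paragraph and give each its own method.

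- **New antibody.** To test whether rituximab prevents de novo antibody, "we will compare titers of autoantibodies (or DSA) between the rituximab and control groups". This is a contrast of the randomised arms.
- **Existing antibody.** The plan first concedes that "the absolute numbers of patients in each group with preexisting autoantibodies or DSA is anticipated to be small (thus limiting power", and then says "we will compare and report pre vs post-transplant titers in each case to determine if rituximab impacts preexisting antibody". The comparison named is before against after.

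Later in the same sections, for DSA and autoantibody results in general, the authors doubt that one model with treatment, time and their interaction can be fitted, and conclude that "we will describe the treatment effect over the course of the follow-up period". No model, contrast or subset is named there. For flow cytometry, by contrast, SAP 7.4 is explicit that B and T cell "fractions will be compared between treatment groups within a repeated measures mixed model framework".

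On background treatment, protocol 7.1.1.1 states: "All subjects will receive Thymoglobulin® induction therapy". Tacrolimus, MMF and steroids are also common to both arms (SAP 6.2). Protocol 9.1.2 defines a positive autoantibody result by a cutoff above the mean of normal subjects, starting at one standard deviation.

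**The concern.** Whether rituximab affects existing antibody is a causal question, and a before-and-after change in treated children does not isolate the drug. Two other things can move the titre.

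- **Shared change.** Every child has a transplant and four other immunosuppressants between the two samples. If these lower titres, the rituximab arm falls with no help from rituximab. If surgery and graft injury raise them, a real rituximab effect can be masked.
- **Regression to the mean.** The group is selected because the first value is above a cutoff. Later values are lower on average even if nothing has happened.

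The placebo arm has both of these and lacks only the drug, so the difference between arms is the quantity that answers the question. If the plan's wording means that pre/post results are shown for each arm, two separate within-arm results still do not estimate or test that difference.

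What is at stake is part of the mechanism. Secondary objective 1 is the effect of rituximab on post-transplant immunity, and 33–44% of comparable children had autoantibody before transplant (protocol 2.4).

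**Working it through.** The documents give no sample size, power, error rate or test for this question, so there is no stated figure to reproduce. The steps below show direction and rough size.

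**1. Children who contribute.** There are 50 randomised 1:1 (protocol 3.1), so 25 per arm. Prevalence before transplant comes from the CTOTC-03 data in protocol 2.4.

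- ColV: 25 × 0.33 = 8.25 per arm
- kα1T: 25 × 0.44 = 11.0 per arm
- Class I DSA: 25 × 0.03 = 0.75 per arm, and the chance of at least one in an arm is 1 − 0.97^25 = 53%
- Class II DSA: 25 × 0 = 0

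**2. Expected regression to the mean.** Assume normal log titre in SD units, with positives being the top fraction p. Their mean baseline is m = φ(z)/p, where z is the cutoff. With pre/post correlation r, the expected fall with no drug effect and no shared change is (1 − r) × m.

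- p = 0.33: z = 0.44, m = 0.362/0.33 = 1.10. The fall is 0.11 SD at r = 0.9, 0.22 at 0.8, 0.33 at 0.7 and 0.55 at 0.5.
- p = 0.44: z = 0.15, m = 0.394/0.44 = 0.90. The fall is 0.09, 0.18, 0.27 and 0.45 SD.

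**3. Consequence for a test.** Trials were simulated with no rituximab effect, 8 or 11 positives per arm, and two-sided 10% error to match the plan's 90% intervals. Post titre = r × baseline + noise − shared shift. Two analyses were compared: a paired t-test within the rituximab arm, and ANCOVA between arms adjusted for baseline.

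| Setting, no drug effect | Paired test, rituximab arm | ANCOVA between arms |
|---|---|---|
| No shared change, r = 0.9 | 17% reject | about 10% |
| No shared change, r = 0.8 | 23–24% reject | about 10% |
| No shared change, r = 0.7 | 31% reject | about 10% |
| No shared change, r = 0.5 | 45–46% reject | about 10% |
| Shared fall of 0.25 SD, r = 0.5 to 0.9 | 62–77% reject | about 10% |
| Shared rise of 0.25 SD, r = 0.8 to 0.9 | 0.3–4% false falls | about 10% |
| Shared rise of 0.25 SD, r = 0.7 | 6–9% false falls | about 10% |
| Shared rise of 0.25 SD, r = 0.5 | 17–21% false falls | about 10% |

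**4. The opposite error.** A shared rise of 0.25 SD and a true rituximab effect of −0.25 SD sum to zero. The pre/post comparison then shows only regression to the mean and says nothing about the drug. Both arms carry the same rise, so the between-arm difference is still −0.25 SD.

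**5. Separate tests in each arm.** With regression to the mean alone and no drug effect, a significant fall with rituximab but not with placebo arises in 13–25% of trials.

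The correlations, shifts, normality and both tests are assumptions.

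**The case against.** The strongest reply is that the plan is thin here but not blind to the control arm. The sentence speaks of patients in each group, concedes that power is limited, and promises to report titres case by case, which may mean no more than a listing of pre/post values for both arms. The de novo hypothesis is tested by a titre comparison that is not expressly limited to baseline negatives. The general statement that "we will describe the treatment effect over the course of the follow-up period" covers all DSA and autoantibody data, and a treatment effect in a two-arm trial is a between-arm quantity. Much of this stands. No paired test is named, and an informal look across arms is possible. But none of these sentences gives a contrast, an adjustment or an interval for children positive at baseline, and the only method attached to the existing-antibody question is before against after.

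A second reply is that the shared change may be upward. Protocol 2.4 reports frequent new DSA and autoantibody after transplant. Those are new antibodies, so the direction in children already positive is unknown. This also stands: the 62–77% figure applies only if the shared change is a fall.

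Three stronger readings are tempting, and the documents do not support them.

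- A reader might infer that the placebo arm is left out of the analysis. The text does not say so.
- A reader might infer that the trial will usually credit rituximab with a false fall. That depends on a shift and a correlation that the documents do not give.
- A reader might take the adult data in protocol 2.4 as evidence that rituximab does nothing to existing antibody. DSA cleared in 27 of 44 (61%) given IVIG plus rituximab, and "An additional 17 patients were treated with IVIG alone and 11 (65%) cleared the DSA". Those patients were adults, not randomised, and all given IVIG, which this trial restricts (protocol 7.3). The comparison shows why a control is needed. It gives no background clearance rate for this trial.

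**Conclusion.** The point holds as a gap in specification. A causal question about rituximab is attached to a pre/post comparison, with no between-arm contrast stated for children positive before transplant. A shared change or regression to the mean could be read as a drug effect, and a shared rise could hide one. The need for a between-arm contrast does not depend on the simulation, because it follows from common background treatment and selection on a high first value. The size does depend on it: 17–46% false rejections from regression to the mean alone (correlation 0.9 to 0.5), 62–77% with a shared 0.25 SD fall, and 0.3–21% false falls with a shared 0.25 SD rise, against about 10% for the adjusted comparison of arms. These rates illustrate the risk and do not predict how this plan will behave.

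The analysis is secondary mechanistic in the SAP and exploratory in protocol 13.4.5. No primary, clinical or safety conclusion rests on it. The change is worth making because it is cheap and the control data will already exist.

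**What to change.** In SAP 7.4 and protocol 13.4.5, replace the pre/post sentence with a between-arm estimate:

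- **Population.** ITT subjects positive for the given autoantibody before transplant, with ColV and kα1T analysed separately.
- **Estimate.** The rituximab-minus-placebo difference in post-transplant antibody, adjusted for the pre-transplant value, with a 90% CI.
- **Method.** ANCOVA on log titre, or its repeated-measures equivalent, if continuous titres are available. If only the binary or ordinal results described in SAP 7.4 exist, use an ordinal or exact method, such as the risk difference in becoming negative with an exact 90% CI.
- **Pre/post values.** Report them by arm as description, and draw no conclusion about rituximab from a within-arm change.
- **Pre-existing DSA.** Give a listing only, since about 0.75 class I positives are expected per arm and no model can be fitted.

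The cost is a change of wording in both documents and one model per autoantibody, on sera already scheduled before and after transplant in both arms (protocol Appendix 1). The downside is a wide interval from about 8 to 11 children per arm. In the same simulation, with a true 0.5 SD effect, ANCOVA has power of 28–68% with 8 per arm and 36–81% with 11, as the correlation goes from 0.5 to 0.9. The result should therefore be presented as estimation.
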